Dispense cardiac monitor and supplies. Train subjects on the use of cardiac monitor.					x (if applicable)								
Instruct subject to contact the investigational center staff in the event they experience problems with their study devices (refer to Section 11.8).		x											
Assess subjects for the occurrence of any adverse events or device deficiencies (see Section 11) at each visit and document on the appropriate source and record event(s) on the appropriate eCRF.		x	x	x	x	x	x	x	x	x	x	x	x
Based on data surveillance reports as available (uploaded to BOX by sponsor), discuss subject compliance (e.g. meal logging, CGM use, sleep and insulin tracking etc.)			x	x	x		x	x	x	x	x	x	
Schedule next visit/phone call date and time.	x	x	x	x	x		x	x	x	x	x	x	

Medtronic Business Restricted

CIP331 Clinical Investigation Plan

D00323255

Version

Page 48 of 78

Medtronic

	Phase 1						Phase 2						
	Visit 1 (Office)	Visit 2 (Office)	Visit 3 (Phone)	Visit 4 (Office)	Visit 5 (Office or Phone)	Visit 6, EOS (Office)	Visit 6 (Office)	Visit 7 (Phone)	Visit 8 (Phone)	Visit 9 (Office)	Visit 10 (Phone)	Visit 11 (Phone)	Visit 12, EOS (Office)
Visit Window	Enrollment	Up to 14 Days After Visit 1	Day 10 (± 4 Days) After Visit 2	Day 30 (± 7 Days) After Visit 2	Day 60, Day 60 (± 7 Days) After Visit 2	Day 100 (± 7 Days) After Visit 2	Day 90, (± 14 Days) After Visit 2	Day 120 (± 14 Days) After Visit 2	Day 150 (± 14 Days) After Visit 2	Day 180 (± 14 Days) After Visit 2	Day 210 (± 14 Days) After Visit 2	Day 240 (± 14 Days) After Visit 2	Up to Day 280 (± 7 Days) After Visit 2
Discuss and schedule with subject the targeted 7-consecutive days of meal logging to occur before next.		x		x	x		x	x	x	x	x		
Determine if subject will participate in Phase 2				x									
Return cardiac monitor and supplies						x (if applicable)							
Return study devices, unused supplies, and study guides from subject (Refer to Table 1)						x							x
Administer EOS questionnaire					x								x
An Exit eCRF will be completed at this visit. The investigational center staff will complete the Exit eCRF even if the study devices are not worn for the required time or if the subject self-removed one or more study devices at home.					x								x
Enter data into eCRFs as appropriate.	x	x	x	x	x	x	x	x	x	x	x	x	x
General Reminders													
Inform subject that observation or assistance by sponsor may occur at any time during the study	x												
Remind subject to bring insulin pen to Visit 2	x												
Remind subjects to bring in the study meter and control solution for quality control testing to each visit		x	x		x		x	x	x		x	x	

Medtronic Business Restricted

CIP331 Clinical Investigation Plan

D00323255

Version

Page 49 of 78

Medtronic

	Phase 1						Phase 2						
	Visit 1 (Office)	Visit 2 (Office)	Visit 3 (Phone)	Visit 4 (Office)	Visit 5 (Office or Phone)	Visit 6, EOS (Office)	Visit 6 (Office)	Visit 7 (Phone)	Visit 8 (Phone)	Visit 9 (Office)	Visit 10 (Phone)	Visit 11 (Phone)	Visit 12, EOS (Office)
Visit Window	Enrollment	Up to 14 Days After Visit 1	Day 10 (± 4 Days) After Visit 2	Day 30 (± 7 Days) After Visit 2	Day 60, Day 60 (± 7 Days) After Visit 2	Day 100 (± 7 Days) After Visit 2	Day 90, (± 14 Days) After Visit 2	Day 120 (± 14 Days) After Visit 2	Day 150 (± 14 Days) After Visit 2	Day 180 (± 14 Days) After Visit 2	Day 210 (± 14 Days) After Visit 2	Day 240 (± 14 Days) After Visit 2	Up to Day 280 (± 7 Days) After Visit 2
Remind subject to keep applicable devices charged			x	x	x		x	x	x	x	x	x	
Remind subject to check on the adequacy of their supplies			x	x	x		x	x	x	x	x	x	
Remind subject to contact the investigational center staff or Medtronic support line in the event they experience problems with their study devices (refer to Section 11.8).		x	x	x	x		x	x	x	x	x	x	
Provide subjects with the opportunity to bring up study-related questions and concerns (e.g. sensor related issues).	x	x	x	x	x	x	x	x	x	x	x	x	x

*All concomitant medications collected except vitamins and supplements.

Medtronic Business Restricted

9.3 Unscheduled Visit

If the subject visits the investigational center outside of the scheduled study visits, a Visit eCRF will be completed to document the reason for the unscheduled visit.

Examples of reasons for an unscheduled visit and completion of the appropriate eCRF include, but are not limited to:

- Replacement of a study sensor(s) within 24 hours of the initial sensor insertion if there is need of replacement.
- Subject requests investigational center staff to examine sensor insertion site(s)
- Subject has an AE and/or device deficiency that requires a visit prior to next scheduled visit
- For subject re-training (e.g. subject expected activities and/or app use)

9.4 Subject Consent

Informed Consent and Assent will be obtained in accordance with the Code of Federal Regulations (CFR) Title 21, Part 50. Prior to entry into the study, the California Experimental Subject's Bill of Rights (if applicable), the Institutional Review Board (IRB) and Medtronic approved ICF and assent form and an Authorization Form required by the Health Insurance Portability and Accountability Act (HIPAA) will be presented to each subject to review and sign as applicable. The subject and their parent or guardian will be offered the opportunity to review these documents away from the investigational center.

The following will be provided to or explained to the subject and their parent or guardian by the investigator or designee: the purpose and duration of the study, the requirements expected to be adhered to by the subject during the study and the potential risks/potential benefits associated with participation in the study. Every attempt will be made to answer the subject's and their parent's or guardian's questions during the informed consent and assent process. The language used shall be as non-technical as possible and must be understandable to the subject or their parent or guardian.

The subject must have ample time and opportunity to read and understand the ICF, to inquire about details of the study, and to decide whether or not to participate in the study. All questions about the study should be answered to the satisfaction of the subject.

Neither the investigator, nor the investigation center staff shall coerce or unduly influence a subject or their parent or guardian to participate or to continue to participate in the clinical study. The informed consent and assent process shall not waive or appear to waive the subject's rights.

Subjects will complete California Experimental Subject's Bill of Rights (if applicable), the HIPAA Form, and the ICF and assent form. The consenting process must be documented in the subject's source documents. The subject and their parent or guardian will receive copies of the documents. A subject's participation in study procedures cannot begin before the consent process has been properly executed.

Medtronic Business Restricted

When the subject decides to participate in the study, the ICF must be signed and personally dated by the subject and investigator or authorized designee, as required by the ICF.

Medtronic will inform the investigators whenever information becomes available that may be relevant to the subject's confirmed participation in the clinical study. The investigator or his/her authorized designee should inform the subject and their parent or guardian in a timely manner.

Medtronic will revise the written ICF and assent form whenever new information becomes available that may be relevant to the subject's confirmed participation in the clinical study. The revised information will be sent to the investigator for approval by the IRB. After approval by the IRB, a copy of this information must be provided to the participating subjects, and the informed consent and assent process as described above needs to be repeated.

If the ICF and assent form are amended during the course of the study, the IRB will determine:

- Whether or not active subjects and their parent or guardian should be re-consented at their next visit
- Whether or not subjects who have completed the study at the time of the amendment should repeat the informed consent and assent process.

Subjects and their parent or guardian will be informed that qualified personnel from the investigational center, the sponsor (Medtronic), agencies such as the FDA and/or the IRB, may have access to the clinic records that reveal their identity and health care information.

The investigational center must report the following informed consent and assent violations to their IRB and sponsor:

- Failure to obtain informed consent and assent from subject and their parent or guardian
- Failure to obtain informed consent and assent prior to performing one or more study procedures.
- Failure to maintain ICFs and assent forms on file for all subjects who have provided informed consent.
- Use of an ICF and assent form that has not received approval from the IRB.
- Use of an incorrect version of the ICF and assent form.

9.5 Medical Oversight

In order to conduct the study, investigational center staff that have the appropriate medical training is required.

9.5.1 Medical Staff

A physician (or designee) who has managed patients on both CGM and intensive insulin therapy will be included in the study as the principal investigator.

Medtronic Business Restricted

9.5.2 Qualification

The investigator (or designee) will need to have one of the following qualifications: endocrinology fellowship or management in patients with diabetes in a clinical practice. The provider must be qualified to treat diabetic emergencies.

9.5.3 Experience

Investigator (or designee) must also have at least one-year experience in managing patients with insulin carbohydrate ratios and insulin sensitivity ratios in his/her practice.

9.6 Glucose and Glycemia Measurements

During the course of the study, the subjects' BG levels and SG levels will be assessed using the methods outlined in this section.

9.6.1 Daily Blood Glucose

Values will be assessed during the study by all subjects using the study meter. The control solution test will be performed following the manufacturer's user guide. Subjects will be trained on the use of the study meter per the manufacturer's instructions.

9.6.2 Sensor Glucose Values

Sensor Glucose (SG) data will be collected by subject's Guardian Connect system.

9.7 Recording Data

Data, excluding uploads, will be captured on eCRFs using Oracle Clinical Remote Data Capture (OC-RDC) module. Original eCRFs will not be considered as source data and supporting documentation will be required.

Electronic device data will be collected from the Guardian Connect transmitter, wearables, smartphone apps, smart pen cap/smart pen, cardiac monitor, and study meter. Electronic data collected will be collected by smartphone apps and stored on their respective data cloud. Data from all apps used in this study will be sent to the Nutrino data servers, where it will be processed. Klue video capture data files will be sent to the sponsor electronically using the internet and a secure cloud-based site. The CareLink software system uses TLS technology, which encrypts all data it stores (21 CFR Part 11 compliant). Electronic device data will be collected from the transmitters utilizing the respective software.

The Investigator will ensure that all eCRFs are completed promptly, completely, and accurately. Medtronic will provide detailed instructions to assist with eCRF completion. In the event of data discrepancies, investigational centers will be asked to resolve queries electronically in the OC-RDC system; otherwise, irresolvable data-related issues will be routed to the sponsor for review and final

Medtronic Business Restricted

disposition. An audit trail is maintained in OC-RDC to capture any corrections or changes of the eCRFs. System backups for data stored in the Oracle Clinical system will be consistent with Medtronic Standard Operating Procedures (SOPs).

Medtronic will only consider eCRFs to be complete when all discrepancies between source data and eCRF have been resolved and applicable eCRF content has been reviewed by a Study Monitor. In addition, specific eCRFs must also be reviewed and electronically signed by the Investigator, indicating his/her agreement with the accuracy of all recorded data. It is expected that the Investigator and his/her staff will cooperate with the monitoring team and provide any missing data in a timely manner.

9.8 Deviation Handling

A deviation is any instance(s) of failure to follow, intentionally or unintentionally, the requirements of the CIP. It is expected that the investigator will conduct this clinical trial in compliance with the CIP and all applicable regulations governing the conduct of clinical research involving human subjects. Failure to do so could result in one or all of the following:

- Investigational center disqualification
- Notification to the regulatory authorities/IRB depending on the severity of the deviation and reporting requirements

The investigator should not implement any deviation from, or changes to, the CIP without agreement by the sponsor and prior review and documented approval/favorable opinion from the IRB, except where necessary to eliminate an immediate hazard(s) to trial subjects or when the change does not affect the scientific soundness of the plan or the rights, safety, and welfare of the subjects.

9.8.1 Documenting Requirements for Study Deviations

9.8.1.1 Unplanned CIP Deviations

The investigator may encounter the need to deviate from the CIP when necessary to protect the safety, rights or well-being of a subject in an emergency or in unforeseen situations beyond the investigator's control (e.g., subject failure to attend scheduled follow-up visits, inadvertent loss of data due to computer malfunction, inability to perform required procedures due to subject illness).

Deviations from the CIP, regardless of the reason should be documented as soon as possible, after the deviation occurs or is identified. This documentation should include deviation date, description of the deviation, the reason for deviation, and the corrective action. Refer to Table 3 for reporting timelines for emergency deviations.

CIP deviations should be reported as follows:

- a) To the IRB for notification/acknowledgement;
- b) To the sponsor and, if required;
- c) To the applicable regulatory agency (reported by sponsor)

Medtronic Business Restricted

9.9 Reporting Requirements for Study Deviations

All study deviations must be reported on the eCRF regardless of whether medically justifiable, an inadvertent occurrence, or taken to protect the subject in an emergency. The date and reason for each deviation will be documented (21 CFR 812.140 Records).

The following examples are deviations that could impact subject safety, affect the integrity of study data and/or affect subject's willingness to participate in the study. These deviations are significant and require immediate sponsor notification upon investigator awareness:

- Failure to obtain informed consent and assent, i.e., there is no documentation of consenting
- Informed consent and assent obtained after initiation of study procedures
- Continuation of a subject who did not meet all inclusion/exclusion criteria
- Performing study procedure not approved by the IRB
- Failure to inform IRB and sponsor of reportable AEs (see **Section 11**)
- Investigational study device dispensed without obtaining informed consent and assent

Reporting of all other study deviations should comply with:

- IRB policies and/or
- local laws and/or
- regulatory agency requirements

They must be reported to Medtronic as soon as possible upon the center becoming aware of the deviation. Refer to Investigator Reports, Table 3, for specific deviation reporting requirements and timeframes for reporting to Medtronic, IRB, and regulatory agency (if applicable).

9.9.1 Analyzing Deviations

Medtronic is responsible for reviewing deviations, assessing their significance, and identifying any additional corrective and/or preventive actions (e.g. amend the CIP, conduct additional training, terminate the investigation). Repetitive or serious investigator compliance issues may result in initiation of a corrective action plan with the investigator and investigational center, and in some cases, necessitate suspending enrollment until the problem is resolved or ultimately terminating the investigator's participation in the study.

9.10 Subject Exit, Withdrawal or Discontinuation

Subjects may choose to withdraw from the study at any time by notifying investigational center staff of their intent.

If a subject chooses to end his or her study participation or if the subject is removed from the study at the Investigator's discretion or for failure to meet the study requirements, the reason for withdrawal

Medtronic Business Restricted

must be documented. All study devices and supplies must be returned (as applicable) and documented both in source documents and on an eCRF.

Subjects may also be withdrawn from the study at the discretion of the Investigator. A subject will be withdrawn from the study if:

- In the opinion of the investigator, the subject's health or safety would be compromised by continuing in the study
- In the opinion of the investigator, it is in the subject's best interest to discontinue participation in the study
- During the course of the study, subject begins participation in another investigational study (drug or device).
- The subject is found to no longer meet all inclusion criteria, or is found to meet one or more exclusion criteria
- The subject fails to comply with one or more study requirements
- During the study, (female) subject becomes pregnant.

Documentation of the reason(s) leading to subject withdrawal will be kept in the subject's source documentation.

Medtronic Business Restricted

10 Risks and Benefits

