
Medtronic Business Restricted

	
use the Guardian Connect system, track insulin delivery via the smart pen or pen caps, track sleep, track activity, and respond to prompts (as applicable). Subjects are instructed to use information from the Guardian Connect app in an adjunctive manner, per product labeling. The general study timeline of activities is as follows:
 
Phase 1
 
▪ Day 1-30 
For 7 consecutive days during Days 8-27 (to ensure there is sufficient time for site to review surveillance report prior to Visit 4), each subject should log food consumption (meals, drinks and snacks) concurrent with CGM, sleep and activity tracking, insulin delivery data collection, and medication. The subject will be asked to check a fasting SMBG using the study meter after a minimum of 8 hours of fasting for two mornings during the week they log their food.
 
▪ Day 31-90 
Each subject should log food consumption for a minimum of 7 consecutive days per month.
 
Day 100 will be the End of Study (EOS) unless the subject is participating in Phase 2. If EOS, devices should be returned, wearables reset to factory settings, and subject's participation in the study will be completed.
 
Phase 2
 
▪ Day 91-280 
Some subjects 18 years of age or older will continue to provide data for an additional 180 days based on adherence to study requirements demonstrated during Phase 1. Subjects will be asked to log food consumption (meals, drinks and snacks) for a minimum of 7 consecutive days per month concurrent with CGM, sleep and activity tracking, insulin delivery data collection, and medication. At End of Study (EOS, Day 280 (± 7 Days)) devices should be returned, wearables reset to factory settings and subject's participation in the study will be completed.

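### Does the non-compliance bullet in Section 9.10 oblige sites to withdraw a subject after a single lapse?

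*Protocol*

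**What the plan says.** Section 9.10 of the protocol is the only subject stopping rule; the Synopsis simply refers to it. It first covers a subject who leaves by choice or is "removed from the study at the Investigator's discretion or for failure to meet the study requirements", and asks that the reason be documented. It then says the investigator may withdraw subjects at his or her discretion. The next sentence begins "A subject will be withdrawn from the study if" and introduces six bullets. The first two are expressly matters of the investigator's opinion. The fifth is "The subject fails to comply with one or more study requirements", with no such qualifier and no list of the requirements meant.

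Three other places bear on lapses:

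- Section 9.8: "A deviation is any instance(s) of failure to follow, intentionally or unintentionally, the requirements of the CIP".
- Section 9.8.1.1 gives as examples of unplanned deviations "subject failure to attend scheduled follow-up visits" and "inability to perform required procedures due to subject illness", to be documented with the corrective action.
- The Synopsis and Section 5 let some adults continue into Phase 2 "based on adherence to study requirements demonstrated during Phase 1".

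**The concern.** Taken word for word, the bullet is a one-lapse rule. A skipped week of food logging or a missed visit would require withdrawal, and a site that kept the subject would itself be departing from the protocol. The rest of the plan reads as though subjects with lapses stay. In particular, choosing Phase 2 subjects by Phase 1 adherence achieves little if everyone who lapsed has already gone.

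With up to 30 centers, some might apply the bullet strictly and others loosely. The later Phase 1 time-in-range data would then come from a more adherent subset, withdrawal counts would partly reflect site practice, and the minimum of 260 completers could be harder to reach. Reporting the withdrawals would reveal this but would not recover data that were never collected.

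**Working it through.** **Is the bullet mandatory?** Two features of Section 9.10 point that way: the verb that opens the list, and the earlier phrase "removed from the study at the Investigator's discretion or for failure to meet the study requirements", which sets failure to meet requirements beside discretion as a separate ground. Two point the other way. The sentence immediately before the list is about investigator discretion, and nobody except the investigator is named to judge whether a subject has failed. The text leaves the question open.

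**Is a threshold missing?** Not strictly, since one or more is a threshold of one. What is unstated is which duties count and what degree of lapse is a failure. Inclusion criterion 5 in Section 7.3 has subjects agree to follow the protocol's requirements. Section 9.4 says those expected of the subject are explained at consent. The consent materials are under separate cover and may list them.

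**Do other passages contradict withdrawal?**

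- Phase 2 entry (Synopsis, Section 5): real tension. A strict one-lapse rule would make this criterion largely redundant.
- Missed visits and illness (Section 9.8.1.1): an awkward fit, but recording a deviation does not exclude withdrawal.
- Compliance discussions and re-training visits (Sections 9.1.1, 9.2 and 9.3): compatible with either reading, since both can precede a judgement that the subject has failed.
- Exit form (visit activities table, Section 9.2): staff "complete the Exit eCRF even if the study devices are not worn for the required time". A withdrawn subject needs an exit form too, so this does not imply retention.
- Fasting fingerstick: worded as a request in the Synopsis, a requirement in Section 5 and an instruction in Section 9.2. Nothing ties any of these to withdrawal.

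**Room for loss.** Inputs are the enrollment cap of 500 and the minimum of 260 completers (Synopsis; Section 7.1).

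500 − 260 = 240; 240 / 500 = 0.48.

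This is the tolerance for loss from any cause if enrollment reaches the cap.

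**What a literal rule would do (illustration only).** Suppose each of *k* requirements is met independently with probability *p*. Both values are assumptions. Expected lapse-free subjects = 500 × *p*^*k*, and reaching 260 needs *p* ≥ (260/500)^(1/*k*) = 0.52^(1/*k*).

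| *k* | Example | *p* needed | *p* = 0.95 | *p* = 0.90 |
|---|---|---|---|---|
| 3 | three monthly food-logging weeks | 0.804 | 429 | 365 |
| 10 | those, two fasting fingersticks, Visits 2 to 6 | 0.937 | 299 | 174 |
| 90 | one daily duty for 90 days | 0.993 | 5 | 0 |

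Under a literal rule with even one daily duty, the 260 target would need compliance above 99% on each day. A rule that would so easily defeat the study's own target is unlikely to be what the sponsor meant or what sites would do. The table does not estimate what will happen.

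**Which planned results depend on it?** Protocol Sections 13.6 to 13.8 and SAP Sections 7.9 and 7.10 plan descriptive summaries only. SAP Section 7.1.3 keeps every enrolled subject in the safety population. Neither document restricts the time-in-range summary to completers.

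**The case for a change.** The best case for amending runs as follows. The missing opinion qualifier and the phrase that separates requirement failure from discretion make the mandatory reading at least respectable. If the text can be read both ways, up to 30 centers may do so. Adherence selection is planned for Phase 2 only, and a strict reading would bring it into Phase 1. Clarifying the text needs only a sentence or two.

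The ambiguity and the tension with the Phase 2 criterion both stand. The consequence is not shown. A link between adherence and glycemic control is an assumption that the documents do not address. Divergence between centers has a central check, because the sponsor supplies the data surveillance reports used at follow-up visits and, under Section 9.9.1, reviews deviations, judges their significance and can call for more training. Withdrawal reasons (Protocol 13.2, SAP 7.1.1), deviations (Protocol 13.5, SAP 7.1.2) and available data (Protocol 13.7, SAP 7.9.2) are all reported.

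The remedy is also thin. It would ask the sponsor to define a term and to choose between mandatory and discretionary withdrawal. The documents do not settle that choice, and neither answer is shown to improve a planned result. Under Section 15.10, even an administrative amendment goes to the IRB.

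**Conclusion.** The wording is loose and, read strictly, sits badly with the Phase 2 adherence criterion and with the handling of missed visits as deviations. It is missing detail in a standard withdrawal bullet, which investigators can be expected to apply with judgement. The study collects data for product development and reports descriptive statistics, so no inference, error rate or power is affected.

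The size of any effect is unknown, because the documents give no compliance or withdrawal rate. The 48% figure is overall room for attrition at full enrollment, and the table above rests on assumed compliance and independence. The conclusion assumes that sites do not apply the bullet as a one-lapse rule. If some did, the listed withdrawal reasons would show it, although data lost after withdrawal would stay lost. The passages could be aligned if the protocol is amended for another reason, but this point does not justify an amendment by itself.
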